12.4 Efficacy Analyses

12.4.1 Double-Blind Treatment Phase

All efficacy analyses will be performed on the mITT Population. Results of the Double-Blind Treatment Phase will be reported following database lock once all patients have completed or discontinued the Double-Blind Treatment Phase of the study.

12.4.1.1 Hypothesis Testing Strategy

The study is a Phase 2 proof of concept and is not powered to show statistical significance; therefore, no formal multiplicity adjustment will be done.

All tests will be 2-sided. P-values will be reported for the individual doses, the combined doses, and for all the outcomes.

The following order reflects the endpoints of most interest and greater consideration will be given to successful endpoints higher in the list, particularly when all preceding endpoints have a significant p-value. For the secondary endpoints, interpretation of the results regarding statistical significance will be based on the pattern of results.

Primary Endpoint:

- Change in mean ESS-CHAD (parent/caregiver version) score from Baseline to Week 11 (Visit 5) for the high dose group compared with placebo
- Change in mean ESS-CHAD (parent/caregiver version) score from Baseline to Week 11 (Visit 5) for the low dose group compared with placebo
- Change in mean ESS-CHAD (parent/caregiver version) score from Baseline to Week 11 (Visit 5) for the pooled active doses group compared with placebo

Key Secondary Endpoints:

- Change from Baseline to Week 11 (Visit 5) in Caregiver Global Impression of Severity (CaGI-S) for EDS for the high dose group compared with placebo
- Change from Baseline to Week 11 (Visit 5) in Clinician Global Impression of Severity (CGI-S) for overall clinical status related to PWS for the high dose group compared with placebo
- Change from Baseline to Week 11 (Visit 5) in CaGI-S for EDS for the low dose group compared with placebo
- Change from Baseline to Week 11 (Visit 5) in CGI-S for overall clinical status related to PWS for the low dose group compared with placebo
- Change from Baseline to Week 11 (Visit 5) in CaGI-S for EDS for the pooled active doses group compared with placebo
- Change from Baseline to Week 11 (Visit 5) in CGI-S for overall clinical status related to PWS for the pooled active doses group compared with placebo

Other Secondary Endpoints:

• Change from Baseline to Week 11 (Visit 5) in behavior as measured by the Aberrant Behavior Checklist, Second Edition (ABC-2) for the high dose group compared with placebo

- Change from Baseline to Week 11 (Visit 5) in behavioral and cognitive rigidity as measured by the Montefiore-Einstein Rigidity Scale – Prader-Willi Syndrome (MERS-PWS) for the high dose group compared with placebo
- Change from Baseline to Week 11 (Visit 5) in Psychomotor function as measured by the Cogstate Detection test for the high dose group compared with placebo
- Change from Baseline to Week 11 (Visit 5) in Attention as measured by the Cogstate Identification test for the high dose group compared with placebo
- Change from Baseline to Week 11 (Visit 5) in Working memory as measured by the Cogstate One Back test for the high dose group compared with placebo
- Change from Baseline to Week 11 (Visit 5) in Measure of caregiver burden using the 22item Zarit Burden Interview (ZBI-22) for the high dose group compared with placebo
- Change from Baseline to Week 11 (Visit 5) in behavior as measured by the ABC-2 for the low dose group compared with placebo
- Change from Baseline to Week 11 (Visit 5) in behavioral and cognitive rigidity as measured by the MERS- PWS for the low dose group compared with placebo
- Change from Baseline to Week 11 (Visit 5) in Psychomotor function as measured by the Cogstate Detection test for the low dose group compared with placebo
- Change from Baseline to Week 11 (Visit 5) in Attention as measured by the Cogstate Identification test for the low dose doses group compared with placebo
- Change from Baseline to Week 11 (Visit 5) in Working memory as measured by the Cogstate One Back test for the low dose group compared with placebo
- Change from Baseline to Week 11(Visit 5) in Measure of caregiver burden using the ZBI-22 for the low dose group compared with placebo
- Change from Baseline to Week 11 (Visit 5) in behavior as measured by the ABC-2 for the pooled active doses group compared with placebo
- Change from Baseline to Week 11 (Visit 5) in behavioral and cognitive rigidity as measured by the MERS- PWS for the pooled active doses group compared with placebo
- Change from Baseline to Week 11 (Visit 5) in Psychomotor function as measured by the Cogstate Detection test for the pooled active doses group compared with placebo
- Change from Baseline to Week 11 (Visit 5) in Attention as measured by the Cogstate Identification test for the pooled active doses group compared with placebo
- Change from Baseline to Week 11 (Visit 5) in Working memory as measured by the Cogstate One Back test for the pooled active doses group compared with placebo
- Change from Baseline to Week 11 (Visit 5) in Measure of caregiver burden using the ZBI-22 for the pooled active doses group compared with placebo

12.4.1.2 Missing Data Imputations

No explicit imputation will be performed for the primary analysis; however, the MMRM model will yield unbiased results under the assumption that data are missing at random.

A sensitivity analysis for the primary endpoint (change from Baseline in mean ESS-CHAD [parent/caregiver version] score) will be performed using a hypothetical strategy. In this approach,

the unobserved data following discontinuation for lack of efficacy or AEs will be assumed to follow the placebo distribution at the matching visit, conditioned on the patient's observed data (including Baseline). Missing data after a patient discontinues treatment (for reasons other than lack of efficacy and AE) and intermittent missing data will be assumed to be missing at random. Details for the imputation are provided in this section.

Patients who discontinue early from the Double-Blind Treatment Phase study drug will be asked to return to the clinic for an Early Termination (ET) visit for completion of assessments (schedule of assessments in Appendix 7). The ESS-CHAD (parent/caregiver version) score collected at ET visit will be mapped to be closest analysis visit based on the rules defined in section 9.2. A multiple imputation approach will be utilized for missing data at Visit 3 (Day 22), Visit 4 (Day 50) and Visit 5 (Day 77, Week 11).

Table 7 represents the imputation rules for the primary endpoint sensitivity analysis. Missing data will be imputed using a three-stage multiple imputation (MI) approach.

Table 7: Post-Baseline Values Scenario and Imputation Methods

Study Medication	Analysis Visit			Imputation	
Status	Visit 3	Visit 4	Visit 5	Imputation	
	Present	Missing	Present	Intermittent missing data will be imputed within	
Completed/ Discontinued	Missing	Present	Present	treatment group using MI under a missing at random assumption with observed values at all	
	Missing	Missing	Present	available time points (including Baseline).	
Discontinued	Present	Present	Missing	Missing data after the discontinuation will be	
due to lack of efficacy or due	Present	Missing	Missing	imputed within the Placebo group (regardless of their assigned treatment group) using MI approach with observed values at all available	
to AE	Missing	Missing	Missing	time points (including Baseline).	
Discontinued	Present	Present	Missing	Missing data after the discontinuation will be imputed within treatment group using MI approach with observed values at all available time points (including Baseline).	
due to any reason but lack of efficacy or	Present	Missing	Missing		
AE	Missing	Missing	Missing		

Abbreviations: AE = Adverse Event; MI = Multiple Imputation.

Note: Multiple imputation method is performed using the analysis visits, i.e., if the nominal result is missing, and there is an unscheduled result or if the ET result falls within the visit window that assessment will be used at that visit.

Step 1. Monotone Missing Pattern: Intermittent missing data will be imputed within treatment group using MI under a missing at random assumption with observed values at all available time points (including Baseline).

- a. From the analysis dataset containing the ESS-CHAD (parent/caregiver version) results, select all the patients (regardless of the discontinuation reason and status). The dataset will contain indicators variables for subject ID: SUBJID, planned treatment: TRTP, Baseline results: BASELINE, Visit 3 results: VISIT3, Visit 4 results: VISIT4 and Visit 5 results: VISIT5) and there will be one record per patient. Before transposing the dataset to get the required structure, if there are multiple non-missing records for a patient, select the record to include as per the rules defined in section 9.2.
- b. Using this dataset with treatment as covariate, imputed datasets (called imputations) will be produced using the Markov Chain Monte Carlo (MCMC) method implemented with the SAS MI procedure. The imputed datasets will contain the observed value (where it was not originally missing) or imputed values as per the model (for missing observations). The values imputed by MCMC method for the missing values will be used for patients who completed the treatment phase but have monotone patterns of missing data.

Step 2. Missing data for patients who discontinued for other reasons (i.e., not due to lack of efficacy or AE): Missing data after the treatment discontinuation (i.e., in the 'tail' end) will be imputed within treatment group distribution (intermittent missing data will have been imputed at the previous step). Patients who completed the treatment but have missing values not imputed at the previous step (i.e., at the 'tail' end) will have their missing imputed together with patients who discontinued for other reasons.

- a. Using the dataset created in step 1, select all the patients regardless of the discontinuation status and reason for discontinuation.
- b. Using this dataset, one imputation will be produced using the MCMC method implemented with the SAS MI procedure. The values imputed by MCMC method for the missing values will be used for patients who discontinued treatment for reason other than lack of efficacy or AE.

Step 3. Missing data for patients who discontinued due to lack of efficacy or AE: Missing data after the treatment discontinuation will be imputed using the placebo group distribution, regardless of their assigned treatment group. The control-based pattern imputation will be implemented by breaking the imputation process into a sequence of multiple calls to PROC MI, where each call is intended to impute missing values at one time-point only, so the sequence will be repeated for each visit (Visit 3, Visit 4 and Visit 5).

- a. From the dataset created in step 2 and for the patients who discontinued due to lack of efficacy or AE, set to missing the results that occurred after the last visit performed for those patients (the last visit performed corresponds to the last analysis visit with no missing data prior to imputation).
- b. Split the dataset into 2 datasets:
 - O Dataset 1 includes all the patients in the placebo group (regardless of the discontinuation reason and status) as well as all the patients in the other treatment

groups (low dose pitolisant and high dose pitolisant) who discontinued treatment before Visit 3 due to lack of efficacy or AE.

- o Dataset 2: includes all the other patients.
- c. Using this dataset, one imputation will be produced using a monotone regression controlled for Visit 3 implemented with the SAS MI procedure (variables order will be Baseline and Visit 3). Once the imputation has been performed all patients who discontinued treatment due to lack of efficacy or AE in the active group will have Visit 3 data imputed.
- d. The dataset generated by the MI procedure (step 3c) will be appended to the dataset 2 (step 2b). This dataset will include all the patients.
- e. The previous steps (b to d) are repeated for each visit (Visit 4 and Visit 5).

The datasets created by the MI procedures at each of the above steps will include 20 records (imputations) per patient for each visit, the changes from Baseline will be derived to obtained Visit 3 change from Baseline, Visit 4 change from Baseline and Visit 5 change from Baseline values. The dataset (created at the last step) will be transposed back to have a record per patient and visit and will include the variables to support the sensitivity analysis.

The following options will be used when using the MI procedure:

- For step 1 and step 2, the input datasets for the MI procedure will be sorted by planned treatment group (numeric) and patient. For step 3, the input datasets for the MI procedure will be sorted by patient.
- For step 1 and step 2, the order of the variables in the MI procedure will be Baseline, Visit 3, Visit 4 and Visit 5; a statement by treatment will be included in the procedure.
- For step 3, the order of the variables in the MI procedure will be Baseline, Visit 3 (for all iterations), Visit 4 (from the second iteration) and Visit 5 (for the last iteration).
- The number of imputations will be (nimpute=1) for the step 1 and will be imputation (nimpute=1) for the steps 2 and 3.
- The data sampling will be rounding the number of decimal point available in the raw data.
- The option min and max will be used to force the procedure to resample, so the values fall within the observed/collected values. For the imputations described in step 2, the minimum and maximum values will be set to the minimum and maximum values of all observed data within the considered parameter collected within the Double-Blind Treatment Phase for the randomized patients (regardless of visits and treatment group).
- For step 1, monotone imputation will be selected with chain as multiple for the MCMC imputation.
- For step 2, the MCMC imputation, single chain (chain=single) with full imputation (imputation=full) will be used. There will be burn-in iterations before the first imputation in each chain (nbiter=) and iterations between imputations in a single chain (niter=). Finally, Jeffreys prior (specifies a non-informative prior) will be used (prior=Jeffreys). Upon review of the plots that will be produced by the MCMC statement,

the burn-in iterations before the first imputation in each chain (nbiter) can be increased to if required.

If the algorithm described in one of the steps (or sub-step) cannot be implemented due to insufficient data, the step will be skipped.

The seeds defined in Table 8 will be used to reproduce the proc MI results. Examples of code are provided in Appendix 4.

Table 8: Sensitivity Analysis Primary Endpoint Multiple Imputation Seeds

Endpoint	Step 1	Step 2	Step 3
ESS-CHAD (parent/caregiver version)	121897	121898	121918 (1 st iteration), 221918 (2 nd iteration) 321918 (3 rd iteration)

Abbreviation: ESS-CHAD = Epworth Sleepiness Scale for Children and Adolescents.

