9.2. Determination of Sample Size

The sample size is 60 patients (20 in the lower dose pitolisant group, 20 in the higher dose pitolisant group, and 20 in the placebo group). Prior research suggests that the ESS-CHAD SD falls between 5 to 6; at the lower end of this range, the study would be powered at 80% to detect a difference of 3.9 between the pooled pitolisant groups and placebo group. However, as a proof of concept, statistical separation is not a strict objective of the trial. The proposed sample size will yield a 95% confidence interval of ± 2.7 with an SD of 5 and ± 3.2 with an SD of 6; this will give sufficient precision to inform future studies.

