8.3 Randomization

Eligible patients will be randomly assigned in a 1:1:1 ratio via an interactive voice/web response system (IXRS) to low dose pitolisant, high dose pitolisant, or matching placebo.

Enrolled patients will be allocated a unique patient number in a sequential order by trial site. Following randomization, Harmony Biosciences will provide all study drug in a packed and labeled kit, and the IXRS will identify the kit number to be dispensed to the patient at each relevant visit according to the treatment assigned in the randomization schedule.

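### SAP 12.4.1.2 does not name the imputation number in steps 2 and 3 and repeats a split fixed at Visit 3; followed literally, the sensitivity analysis departs from Table 7 and from valid Rubin combination

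*SAP*

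**What the plan says.** SAP 12.4.1.2 describes a three-step multiple imputation for the sensitivity analysis of the ESS-CHAD primary endpoint.

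- **Data structure.** Step 1 starts from one record per patient. The datasets that the imputation steps produce "will include 20 records (imputations) per patient for each visit", and steps 2 and 3 each take the output of the step before.
- **Options.** "For step 1 and step 2, the input datasets for the MI procedure will be sorted by planned treatment group (numeric) and patient", and for those steps "a statement by treatment will be included in the procedure". "For step 3, the input datasets for the MI procedure will be sorted by patient"; no BY variable is named for step 3. Steps 2 and 3 use nimpute=1. The imputation number is not in any sort or BY instruction.
- **Step 3 loop.** Step 3a blanks the values after the last visit performed for patients who stopped for AE or lack of efficacy. Step 3b puts into Dataset 1 all placebo patients plus those active-arm patients "who discontinued treatment before Visit 3 due to lack of efficacy or AE". Everyone else goes to Dataset 2. Step 3c imputes Visit 3, step 3d appends Dataset 2 (citing step 2b, although the split is made in 3b), and step 3e repeats b to d for Visits 4 and 5.
- **Stated intent.** Table 7 and the opening of step 3 send all missing values after an AE or lack-of-efficacy discontinuation to placebo-based imputation, including for patients with Visit 3, or Visits 3 and 4, observed.
- **Analysis.** SAP 12.4.1.3.4 fits the MMRM to each replicate and combines the results.

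**The concern.** Proper multiple imputation needs a separate parameter draw for each imputed dataset. If a step 2 or step 3 call is not run by imputation number, the MI procedure sees the 20 copies of each patient as independent rows: 20 patients x 20 copies = 400 rows per arm. With nimpute=1 it makes one draw, from a posterior that is far too tight, and uses it for every copy. The spread between imputations then omits most of the parameter uncertainty, and Rubin's variance no longer means what it should.

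The split is a separate problem. An active-arm patient who stops for AE or lack of efficacy after Visit 3 has the later values blanked in step 3a but does not meet the condition for Dataset 1. If that condition is not moved forward, those values are never imputed from placebo. The MMRM then treats them as missing at random, which is the assumption this analysis exists to challenge. It is the only missing-data sensitivity analysis specified for the primary endpoint.

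**Working it through.** **Inputs.** Protocol 9.2 gives the arm sizes: "20 in the lower dose pitolisant group, 20 in the higher dose pitolisant group, and 20 in the placebo group". It also gives an SD of 5 to 6 and a 3.9-point difference. The protocol gives 20 imputations (9.1.3). Neither document states a dropout rate, so 10%, 20% and 30% per arm are assumptions, as are the between-visit correlations of 0.5 and 0.6.

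**The plan's own figures reproduce.** Half-width, pooled 40 versus 20: 1.96 x 5 x sqrt(1/20 + 1/40) = 2.68 and 1.96 x 6 x sqrt(1/20 + 1/40) = 3.22, against the stated 2.7 and 3.2. Power for 3.9 at SD 5 is 81.3% by the normal formula and 80.0% by the noncentral t. The documents give no standard error for the imputation analysis, so that part was simulated.

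**Standard error.** Steps 2 and 3 were simulated as Bayesian regression draws with 20 imputations, followed by ANCOVA at Visit 5, high dose versus placebo, SD 5. Rubin's total variance is T = W + (1 + 1/20)B, where W is the within-imputation and B the between-imputation variance. Each entry below gives the SE run on stacked copies, then the SE run by imputation.

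| Dropout | Mixed: even over visits, half AE/lack of efficacy, correlation 0.6 | Missing-at-random step: all after Visit 3, correlation 0.5 |
|---|---|---|
| 10% | 1.326 vs 1.399 (5% lower) | 1.42 vs 1.51 (6% lower) |
| 20% | 1.386 vs 1.552 (11% lower) | 1.47 vs 1.69 (13% lower) |
| 30% | 1.423 vs 1.711 (17% lower) | 1.50 to 1.51 vs 1.92 (21 to 22% lower) |

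In the mixed setting, B on stacked copies is 0.56, 0.50 and 0.42 of its proper value. W falls too: at 20% dropout the stacked figures imply W of about 1.386^2 - 1.05 x 0.240 = 1.67, against 1.935 when run by imputation, because the residual variance is also drawn from 20-fold rows.

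**Coverage of the 95% interval, missing-at-random step.** Across repeated simulations, stacked coverage was 93.5 to 94.7% at 10% dropout, 92.6 to about 94% at 20%, and about 92% at 30%. Run by imputation it was 95.1 to 95.7%, 96.2% and 97.2%. The stacked SE against the actual spread of the estimate was 1.43 vs 1.45, 1.47 vs 1.57 and 1.50 vs 1.69.

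**Placebo-based step.** With 20% dropout spread evenly and all of it for AE or lack of efficacy, the stacked SE is 1.396 against 1.544 by imputation (10% lower). The actual spread is 1.228, so there is no undercoverage.

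**The split.** With dropout spread evenly over the three visits, 1599 of 2398 simulated active-arm AE/lack-of-efficacy dropouts (0.67) came after Visit 3. At 20% dropout, half for those reasons, the shift toward placebo that is lost is at most 0.20 x 0.50 x 0.67 x 3.9 = 0.26 points. If all dropout is after Visit 3 and for those reasons, the intended analysis gives about 3.6 at 10% dropout and 3.3 at 20%, while the literal text leaves it near 3.9. The losses are 3.9 - 3.6 = 0.3 and 3.9 - 3.3 = 0.6.

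**The case against.** The strongest reply is that the visible prose is not the full program. The section refers to Appendix 4 for the code, and the public copy shows only headings there. Whether each call runs by imputation number is exactly what that code would show. A reader might infer that the plan has no imputation index at all. The documents do not support that: fitting the MMRM to each replicate and combining the results requires one. Nor does step 1 run on stacked copies, and since the sort and BY bullets are shared by steps 1 and 2, the index could have been left out simply because step 1 does not yet have one. This stands, but an index at the analysis stage does not show that the imputation calls use it, and the stated sort orders do not fit a BY statement on it.

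A reader might also infer that later dropouts will certainly go un-imputed. That is too strong. Table 7, the statement that each call handles one time point, the variable order that adds Visit 4 and then Visit 5, and the three separate seeds all point to a loop that moves forward. Repeating b to d word for word would impute Visit 3 three times and never reach Visits 4 and 5. The Visit 3 condition is probably a drafting slip. It still contradicts Table 7, and the SAP advances the variable list without advancing the split.

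Finally, an SE below the intended Rubin SE is not always too small in truth. In the mixed setting the stacked SE against the actual spread was 1.326 vs 1.374, 1.386 vs 1.327 and 1.423 vs 1.385, and with 600 trials each that spread is known only to about 3%. This also stands, and it limits the coverage claim to the missing-at-random step.

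**Conclusion.** The visible rules for steps 2 and 3 are incomplete on the imputation number, and the step 3 split contradicts Table 7. If programmed to the letter, they give a Rubin SE about 5 to 6%, 11 to 13% and 17 to 22% below the per-imputation value at assumed dropout of 10%, 20% and 30%. Coverage in the missing-at-random step is modestly low, at about 92 to 94%, with no clear undercoverage in the placebo-based step. The split would cost up to about 0.26 points of the intended shift at 20% dropout with half for AE or lack of efficacy, and up to about 0.6 only if all of that dropout is after Visit 3 and for those reasons.

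All of this is conditional on the literal reading and on assumed dropout and correlations. The documents do not support saying that the reported intervals will be too narrow, or that the primary result is affected: the primary MMRM uses no imputation, and the study is a proof of concept. The point is worth correcting because this one analysis carries the plan's whole check on missing data.

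**What to change.** In SAP 12.4.1.2:

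1. Sort and run step 2 by imputation number and treatment, and step 3 by imputation number, and keep that number through to the Rubin combination.
2. In step 3b, define Dataset 1 at each iteration as all placebo patients plus active-arm patients who stopped for AE or lack of efficacy before the visit being imputed, with that visit's value blanked in step 3a. Make step 3c refer to the visit being imputed as well.
3. In step 3d, change the pointer from step 2b to step 3b.
4. Confirm that the Appendix 4 code matches.

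The cost is a few words and BY statements, with no new data or procedures. If the code is already right, the change only brings the text into line. If it is not, the sensitivity interval becomes somewhat wider.
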